6.6.1. Concurrent ITP Therapy

- Participants receiving at least 1 permitted concurrent ITP therapy are eligible for the trial, if the dose and schedule have remained unchanged in the last 4 weeks before randomization (ie, visit 1).
- Permitted concurrent ITP medications include corticosteroids, danazol, vinca alkaloids, oral immunosuppressants, dapsone, fostamatinib, and/or oral TPO-RAs (see inclusion criterion 7, Section 5.1).
- Dose and frequency of permitted concurrent ITP therapies should remain unchanged during the trial.

- Exceptions are participants who are receiving concurrent treatment with oral TPO-RAs in whom dose changes are permitted at label-defined platelet thresholds, and participants who are receiving concurrent treatment with fostamatinib, in whom dose changes or stopping of treatment is allowed in label-defined conditions.
- As of week 12, the start or an increase in the dose and/or schedule of permitted concurrent ITP therapy is allowed for participants who have an “insufficient response” (ie, no platelet count of $\geq 30 \times 10^9/L$ in any of the visits during the last 4 weeks). These participants will be considered as “nonresponders” for the primary endpoint analysis. At the discretion of the investigator, the dose and/or schedule of the concurrent ITP therapy can be returned to the baseline levels.
- Participants not receiving concurrent ITP therapy are also eligible for the trial (see inclusion criterion 7, Section 5.1). The washout periods as specified in exclusion criteria 2 to 8 must be followed. See also Section 10.4.
- Any change in concurrent ITP therapy should appropriately be recorded on the eCRF.
- The medical monitor at the sponsor’s designated CRO should be contacted if there are any questions regarding concomitant or prior therapy.

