9.5.7. Other Secondary Endpoint Analyses Not Subject to Alpha Control

The secondary endpoints on overall platelet count and IWG response³ will be analyzed in the same manner as the primary endpoint. The secondary endpoint on extent of disease control will be analyzed in the same manner as the corresponding key secondary endpoint.

The mean changes from baseline in platelet count levels at planned time points and the mean changes from baseline in PRO/QoL at planned time points will be analyzed by means of mixed models for repeated measurements. The model will include fixed effect terms for randomized treatment, baseline platelet level or baseline PRO/QoL, history of splenectomy (yes vs no), and receiving concurrent ITP therapies at baseline (yes vs no). Within-participant correlation will be modeled by assuming an unstructured covariance matrix for the error terms. Least square (LS) means for placebo PH20 SC and efgartigimod PH20 SC will be provided, along with the difference in LS means, 95% two-sided CI, and two-sided p-value.

Time to response (defined as the time to achieve 2 consecutive platelet counts of $\geq 50 \times 10^9/L$) will be analyzed via Cox proportional hazards regression with fixed effect terms for randomized treatment and baseline platelet level. The model will be stratified by history of splenectomy (yes vs no) and receiving concurrent ITP therapies at baseline (yes vs no), at randomization. The hazard ratio for efgartigimod PH20 SC vs placebo PH20 SC will be provided, along with the associated 95% two-sided CI and two-sided p-value. The data will also be displayed using Kaplan-Meier curves and the median time to response will be displayed by randomized treatment arm.

The number of cumulative weeks over the planned 24-week treatment period with platelet counts of $\geq 30 \times 10^9/L$ and $\geq 20 \times 10^9/L$ above baseline will be analyzed in the same way as described for the key secondary endpoint "extent of disease control." Assessment of number of cumulative weeks over the planned 24-week treatment period with platelet counts of $\geq 30 \times 10^9/L$ and $\geq 20 \times 10^9/L$ above baseline within the group of participants with a baseline platelet count of $< 15 \times 10^9/L$ will also be analyzed as described for the key secondary endpoint.

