4.1.2.3 OTHER SECONDARY ENDPOINTS (NOT ALPHA CONTROLLED)

All other secondary endpoints will be analyzed using the FAS on the overall population.

	Statistical Analysis Plan	
ARGX-113-2004	Final analysis	Final 1.0 of 7NOV2023

- 1) Overall Response: Proportion of participants with overall platelet count response defined as achieving a platelet count of $\geq 50 \times 10^9/L$ on at least 4 occasions at any time during the 24-week treatment period.

Derivation: a participant is considered a responder if he/she shows platelet count of at least $50 \times 10^9/L$ on at least 4 analysis visits during the 24-week treatment period. Platelet count after one of the main intercurrent events will be handled in the same way as for extent of disease control (section 4.1.2.2). Missing values not due to intercurrent events will be handled as described in section 4.1.2.5 (approach 1).

- 2) Extent of disease control defined as the number of cumulative weeks until week 12, with platelet counts of $\geq 50 \times 10^9/L$.

Derivation: total number of analysis visits during the treatment phase until week 12 with platelet counts of $\geq 50 \times 10^9/L$. Platelet count after one of the main intercurrent events will be handled in the same way as for extent of disease control (section 4.1.2.2). Missing values not due to intercurrent events will be handled as described in section 4.1.2.5 (approach 1).

- 3) Proportion of participants with overall platelet response until week 12 defined as achieving a platelet count of $\geq 50 \times 10^9/L$ on at least 4 occasions at any time until week 12.

Derivation: a participant is considered a responder if he/she shows platelet count of at least $50 \times 10^9/L$ on at least 4 analysis visits during the first 12 weeks in the treatment period. Platelet count after one of the main intercurrent events will be handled in the same way as for extent of disease control (section 4.1.2.2). Missing values not due to intercurrent events will be handled as described in section 4.1.2.5 (approach 1).

- 4) Mean changes from baseline for platelet count levels. Missing values will only be imputed for the Mixed Model for Repeated Measurements (MMRM). See section 4.1.3.5.

- 5) Mean changes from baseline in PRO/QoL:

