ARGX-113-2004	Final analysis	Final 1.0 of 7NOV2023

- Scale score = mean of all available converted item scores
A scale score cannot be calculated if less than 50% of the items of the scale are answered. Otherwise, scores for missing items will be imputed with the arithmetic average of the non-missing item scores. Converted item scores are not rounded when calculating the scale score.

- 6) Rate of receipt of rescue therapy: number of times rescue therapy is given per month, calculated as $\frac{\text{Total number of occurrences}}{\text{total days in treatment phase}} \times 30.4$

Occurrence: a period of maximum 5 days where 1 or more rescue treatments are administered simultaneously or consecutively to the study participant. The start date/time of the occurrence is the start of the administration of the first rescue treatment. If this period exceeds the maximum of 5 days, a new occurrence will be assigned, with start date/time of the occurrence being the start date 5 days after the initial occurrence start date.

- 7) Proportion of participants for whom dose and/or frequency of concurrent ITP therapies have increased at week 12 or later.

Derivation: a participant is counted if (start date concurrent ITP therapy \geq lower limit ADY of analysis visit corresponding to week 12) AND (dose > previous dose of the specific ITP therapy OR frequency > previous frequency of the specific ITP therapy OR new ITP therapy). Note: Dose and frequency will always be considered in combination (ie, mean daily doses will be compared).

- 8) Time to platelet count response defined as the time to achieve 2 consecutive platelet counts of $\geq 50 \times 10^9/L$.

Derivation: It will be calculated as the difference between the first assessment date at which the condition '2 consecutive platelet counts $\geq 50 \times 10^9/L$ ' is fulfilled, taking into account all platelet count measurements (also the unscheduled ones), and first IMP intake date.

Time to platelet count response (days) = date (first assessment) – first IMP date + 1:

Table 9: Definition for Time to Platelet Count

Response Situation	Time to Platelet Count Response	Outcome ^d
No occurrence of platelet count of $\geq 50 \times 10^9/L$	Date of last available platelet count ^c – first IMP date ^b + 1	Censored
Early discontinuation of treatment (prior to W24) due to lack of efficacy or due to AE ^a	Early treatment discontinuation date – first IMP date ^b + 1	Censored

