Dose and/or frequency of concurrent ITP therapy increased or a new ITP therapy ^a	Concurrent ITP therapy start date – first IMP date ^b + 1	Censored
Platelet count response	Date (first assessment) – first IMP date ^b + 1	Event

^a only applicable if the event (reaching platelet count response) has not occurred before

	Statistical Analysis Plan	
ARGX-113-2004	Final analysis	Final 1.0 of 7NOV2023

- ^b or date of randomization for participants not treated
- ^c or End-of-Study date for participant with no platelet count assessments
- ^d If multiple censoring conditions apply, the earliest censoring date is considered.

In case of rescue therapy, the platelet count cannot be used for 4 weeks after the initiation of the therapy (the initiation of the therapy is the start date/time of the administration of the first rescue treatment for that occurrence). The platelet count will be interpreted as $<50 \times 10^9/L$ for the 4 analysis visits following the initiation of the rescue therapy. Missing values not due to one of the main intercurrent events will be handled as described in section 4.1.2.5 (approach 1).

9) Extent of disease control defined as number of cumulative weeks over the planned 24-week treatment period with platelet counts:

a) $\geq 30 \times 10^9/L$ and at least $20 \times 10^9/L$ greater than the baseline value

Derivation: total number of analysis visits during the treatment phase with platelet counts of $\geq 30 \times 10^9/L$ and (platelet count – baseline platelet count) $\geq 20 \times 10^9/L$. Platelet count after one of the main intercurrent events will be handled in the same way as for extent of disease control (section 4.1.2.2).

Missing values not due to intercurrent events will be handled as described in section 4.1.2.5 (approach 1), but imputing with $\geq 30 \times 10^9/L / < 30 \times 10^9/L$ and not with $\geq 50 \times 10^9/L / < 50 \times 10^9/L$. In the same way, if (platelet count – baseline platelet count) $\geq 20 \times 10^9/L$ for the previous and the next analysis visit, (platelet count – baseline platelet count) will imputed with $\geq 20 \times 10^9/L$, otherwise with $< 20 \times 10^9/L$.

The above will be repeated for the selection of participants where baseline platelet count $< 15 \times 10^9/L$.

b) $\geq 30 \times 10^9/L$ and at least $20 \times 10^9/L$ greater than the baseline value, where baseline platelet count $< 15 \times 10^9/L$.

Missing values will not be imputed.

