Summary statistics will be provided for the different definitions of number of bleeding events in the overall population. A frequency tabulation will be provided of the number and percentage of bleeding events and repeated for the subgroup on sustained platelet count response (week 19 – 24). The overall severity score at each analysis visit and the worst-case overall severity score will be tabulated.

Summary statistics will be provided in terms of actual values and changes from baseline for PRO scores (FACIT-Fatigue, FACT-Th6) and QoL (SF-36, ITP-PAQ) in the overall population. All analysis visits as expected per SoA (including the follow-up phase) will be shown.

Summary statistics will be provided for the rate of receipt of rescue therapy in the overall population. A frequency tabulation will be provided of the number of rescue therapies (occurrences) received.

Frequency tabulations will be provided of the proportion of participants for whom dose and/or frequency of concurrent ITP therapy have increased at week 12 or later.

KM estimates will be provided for time to platelet count response ($\geq 50 \times 10^9/L$ and $\geq 100 \times 10^9/L$) and time to platelet count $\geq 50 \times 10^9/L$ or $\geq 100 \times 10^9/L$ in the overall population. KM curves and median time to platelet count response will be displayed by randomized treatment.

Summary statistics will be provided in terms of actual values and changes from baseline for IPF# and IPF% in the overall population. All analysis visits as expected per SoA (including the follow-up phase) will be shown.

Statistical inference will be conducted as described below. All statistical comparisons will be made using two-sided tests at the 0.05 significance level unless specifically stated otherwise. Sensitivity analyses will be done for the primary and key secondary endpoints by using the PP population (PP-chronic). The primary and first key secondary endpoint will also be repeated by use of approach 2 for imputing missing values as sensitivity analysis. A complementary analysis using the treatment policy strategy will be done on the primary and the first key secondary endpoint. Furthermore, a complementary analysis will be done on the first key secondary endpoint extent of disease control using a Cox proportional hazards regression model.

	Statistical Analysis Plan	
ARGX-113-2004	Final analysis	Final 1.0 of 7NOV2023

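### Time to response: censoring non-responders when treatment stops for lack of efficacy or ITP therapy is escalated makes the Kaplan-Meier response and median look better than they are

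*SAP*

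**What the plan says.** SAP 4.1.2.3, item 8, defines time to response as the time to two consecutive platelet counts of at least 50 × 10⁹/L, using all counts including unscheduled ones. Table 9 gives the censoring scheme:

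- "Early discontinuation of treatment (prior to W24) due to lack of efficacy or due to AE": censored at the date treatment is stopped.
- "Dose and/or frequency of concurrent ITP therapy increased or a new ITP therapy": censored at the start date of that therapy.

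A footnote makes both rows "only applicable if the event (reaching platelet count response) has not occurred before". Another takes the earliest date when several censoring reasons apply. Rescue is not a censoring reason: "In case of rescue therapy, the platelet count cannot be used for 4 weeks after the initiation of the therapy"; counts in that window are read as below 50 and the participant stays at risk.

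Protocol 9.5.7 specifies a Cox model, Kaplan-Meier curves and the median for this endpoint, and sets no censoring rule. SAP 4.1.3 confirms the display: "KM curves and median time to platelet count response will be displayed by randomized treatment".

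On who may escalate, Protocol 6.6.1 has this rule: "the start or an increase in the dose and/or schedule of permitted concurrent ITP therapy is allowed for participants who have an". The condition that follows is a response judged insufficient, meaning no count of 30 or more at any visit in the last 4 weeks, and the rule applies from week 12. The same section separately permits label-based dose changes of oral TPO-RAs and fostamatinib. Protocol 7.1 keeps participants who stop IMP on weekly visits.

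**The concern.** Kaplan-Meier treats a censored participant as having the same future chance of response as those still at risk. That is hard to accept for someone whose treatment was stopped because it was not working, or who qualified for escalation by having no count of 30 or more for 4 weeks. Removing such people from the risk set raises each later step of the curve. The curve then answers neither the question of how many responded before these events nor, credibly, how many would have responded without them. What is at stake is the reading of the curves and the median. The plan names no estimand for this endpoint, and its stated sensitivity analyses cover only the primary and key secondary endpoints.

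**Working it through.** **1. How the same events are handled elsewhere.**

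| Endpoint | Stop for lack of efficacy or AE; escalated or new ITP therapy |
|---|---|
| Primary (SAP 4.1.2.1) | Non-responder, unless response was already achieved |
| Extent of disease control (4.1.2.2) | Later counts read as below 50 |
| Overall response and other count-based responses (4.1.2.3) | "Platelet count after one of the main intercurrent events will be handled in the same way as for extent of disease control" |
| Loss of disease control (Table 8) | Coded as the unfavourable event |
| Time to response (Table 9) | Censored |

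Table 9 is the only one of these that removes the participant without coding a failure.

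**2. Size, by hand.** The plan states no response or event rate for this endpoint (its sample-size figures concern other endpoints), so all inputs here are assumed. Let p be the true proportion responding before such an event, with half of responses before week 12 and half after. Let c be the share of non-responders who have an event, all placed at week 12 for simplicity. The at-risk fraction at week 12 is R = 1 − p/2, the fraction removed is c(1 − p), and

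1-KM at week 24 = 1 − R × [1 − (p/2) / (R − c(1 − p))].

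- Placebo, p = 0.20, c = 0.50: R = 0.90, removed 0.40, left 0.50. 1-KM = 1 − 0.90 × (1 − 0.10/0.50) = 0.28, against a true 0.20.
- Placebo, p = 0.20, c = 0.60: removed 0.48, left 0.42. 1-KM = 1 − 0.90 × (1 − 0.10/0.42) = 0.314.
- Efgartigimod, p = 0.45, c = 0.30: R = 0.775, removed 0.165, left 0.610. 1-KM = 1 − 0.775 × (1 − 0.225/0.610) = 0.511, against a true 0.45.

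**3. The same model with events spread evenly over weeks 12 to 16** (numerical integration for 1-KM, simulation for the hazard ratio):

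| c, placebo / efgartigimod | Responses before week 12 | Placebo 1-KM (true 20%) | Efgartigimod 1-KM (true 45%) | HR under Table 9 |
|---|---|---|---|---|
| 20% / 10% | 50% | 21.8% | 46.5% | 2.5 |
| 30% / 30% | 50% | 23.0% | 50.3% | 2.7 |
| 50% / 30% | 50% | 26.7% | 50.3% | 2.3 |
| 60% / 20% | 50% | 29.5% | 48.3% | 2.1 |
| 50% / 30% | 70% | 24.3% | 48.7% | 2.45 |
| 50% / 30% | 80% | 23.0% | 47.6% | 2.5 |

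If these participants are instead kept at risk to the end, the HR is about 2.7 in every row (2.6 to 2.8 in single runs, which is simulation error).

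**4. The median.** With p = 0.42 and c = 0.50, all at week 12: R = 0.79, removed 0.29, left 0.50. 1-KM = 1 − 0.79 × (1 − 0.21/0.50) = 0.542. Spread over weeks 12 to 16 it is 52.7%. A median is displayed although 42% respond.

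**5. A second model.** Take constant competing hazards over 24 weeks, with C the proportion responding first and I the proportion having an event first. Then 1-KM = 1 − (1 − C − I)^(C/(C+I)).

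- Events commoner on placebo. Placebo, C = 0.10, I = 0.40: 1 − 0.50^0.2 = 12.9% (+2.9 points, ratio 1.29). Efgartigimod, C = 0.40, I = 0.20: 1 − 0.40^0.667 = 45.7% (+5.7 points, ratio 1.14). Cause-specific HR: ln(0.543)/ln(0.871) = 4.41. HR implied by the cumulative proportions: ln(0.60)/ln(0.90) = 4.85.
- Equal event rates, I = 0.30 in both arms, C = 0.15 and 0.50: the corresponding HRs are 5.05 and 4.27.

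Over 18 combinations of assumed rates and timing, 1-KM exceeded the true proportion in both arms every time. The excess was larger on efgartigimod in percentage points in 15 of 18, and larger on placebo as a ratio in 15 of 18.

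**The case against.** **What stands.**

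- An AE stop need not mark a poor responder, and the first row combines AE with lack of efficacy.
- Escalation is not confined to participants with counts below 30 from week 12. Label-based TPO-RA and fostamatinib changes are permitted throughout, and the Table 9 row carries no week-12 limit. The censored group is therefore mixed, and the event timing used above is an assumption.
- Drawing every censored participant from people who never respond is the worst case.
- Handling rescue differently from a lasting change of treatment is not in itself a flaw.
- Censoring does avoid crediting response to the added therapy, but so does the handling proposed here.
- Several additional analyses are redacted, so a supportive version may already exist.
- The endpoint is secondary and outside alpha control.

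**What a reader might infer, and the documents do not support.**

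- *That placebo is inflated more.* No event rates by arm are given, and the answer changes between the ratio and percentage-point scales.
- *That the hazard ratio is simply biased.* With these events censored it is a valid cause-specific HR. It differs from the HR under composite handling because it targets a different quantity.
- *That disagreement with the overall-response proportion would prove the bias.* Overall response needs four analysis visits at or above 50, while time to response needs two consecutive counts from any measurement. They would differ anyway.

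**What does not rescue the curve.** One could say that censoring targets response had the event not occurred. The SAP does not say so, and that reading needs independence between the event and future response, which the insufficient-response rule contradicts. Missing data do not force the choice either, since weekly visits continue after IMP is stopped.

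**Conclusion.** The point holds for the Kaplan-Meier estimates, curves and median. Lack-of-efficacy stops and escalations under the insufficient-response rule are informative censoring, and 1-KM overstates the proportion responding before these events. With assumed true response of 20% and 45%, and 10% to 60% of non-responders censored in weeks 12 to 16, the overstatement is about 2 to 10 points on placebo and 1 to 5 on efgartigimod, or up to 11 and 6 if every event falls at week 12. It shrinks when most responses come before week 12 (placebo 23% to 24% rather than 27% in the 50%/30% case). The Cox HR needs a label rather than a correction: in these scenarios it moves towards 1 when the events are commoner on placebo, and under equal rates it hardly changes in one model and moves away from 1 in the other. The primary conclusion is not affected. The change is worth making because it is cheap and brings the endpoint into line with the other count-based responses.

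**What to change.** In the two intercurrent-event rows of Table 9, keep the participant in the risk set as not responding, do not let later counts create a response, and censor at day 169, the planned end of treatment. Reword the earliest-date footnote so that it does not bring back an earlier censoring date for these participants. 1-KM then estimates the proportion responding before these events. Apply this to the Kaplan-Meier estimates, curves and median and to the Cox model. Keep the present censoring as a supportive analysis, labelled as a cause-specific HR.

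The cost is two table rows, one footnote and a small programming change, with no new data. The downside is a lower displayed response in both arms, with AE stops counted as non-response, as they already are for the primary endpoint unless response came first.
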